### Add Study Organization(s):

### List Study Organizations associated with this protocol:

Primary Dept?	Department Name	
۲	DUHS - Duke Default Department	

### Oncore

### Please select the Library for your Protocol:

This field is used in OnCore. Determines the Reference Lists, Forms, Protocol Annotations, Notifications, and Signoffs available for the protocol. Protocols that require reporting to the NCI (National Cancer Institute), must select the Oncology library.

Oncology

Non-Oncology

### **Protocol Application Type**

### Select the type of protocol you are creating:

Please see additional criteria and information in the policy titled "Reliance on the IRB of Another Institution, Organization, or an Independent IRB" on the **IRB web site**.

- Regular Study Application Most common. The IRB will determine if the study is eligible for expedited review or requires full board review upon submission.
- O Application for Exemption from IRB Review Includes Exempt, Not Human Subject Research, & Not Research.
- C External IRB Application Any study using an external IRB as the IRB-of-Record.
- Trainee Research While Away from Duke Research conducted by medical students overseen by the Office of Curriculum & other student/trainee research away from Duke.
- Individual Patient Expanded Access, Including Emergency Use Use of an investigational product under expanded access, including emergency use of an investigational drug or biologic or emergency use of an unapproved device.

### **Conflict of Interest**

Do any of the participating study investigators or other key personnel (or their immediate family/significant other) have a financial or intellectual interest in, or are receiving compensation from, the sponsor or the drugs, devices or technologies used in this research?

• Yes • O No

Has this conflict been disclosed to the Duke COI Committee?

🖸 Yes 🛛 No

Are any key personnel an inventor of any of the drugs, devices or technologies used in this research?

• Yes O No

Have you filed an Inventor Disclosure Form?

• Yes • O No

Do any key personnel have or anticipate (within the year) any financial relationships (e.g., consulting, speaking, advisory boards, patents, equity, options) that could be perceived to overlap or present a conflict of interest with the current research?

• Yes • O No

### Describe the overlap:

Rose Research Center provides clinical trials services to JUUL Labs. Given his relationship with JUUL, [name] will not be permitted to serve as PI on Duke research that may result in direct commercial advancement of JUUL products. It is not legal to use Duke's non-profit resources to advance the commercial prospects of a for-profit entity unless the research is performed in such a manner that the Public Benefit is assured. While he can in general perform research in fields of science that may ultimately be useful to companies, he will not be permitted to act as PI for any research that results in a direct commercial advancement of JUUL products. The Research Integrity Office (RIO) has reviewed [name] NIH grants, and he may continue to serve as the Duke PI on the NIH award which uses the JUUL ecigarettes and formulated cartridges.

Do any key personnel have a conflict of interest management plan (issued by the Duke University School of Medicine Research Integrity Office) with this company?

• Yes • No

If Yes, please give the name(s) of the relevant personnel.

[name]

### **Oversight Organization Selection**

CRU (Clinical Research Unit) or Oversight Organization Selection:

Please select the CRU.

Psychiatry

The Clinical Research Unit that takes responsibility for this study.

- More information on CRUs can be found on the Duke Office of Clinical Research (DOCR) website, http://docr.som.duke.edu
- Questions concerning CRU selection should be directed to [contact].
- For questions about the Campus Oversight Organization, please visit **Campus Oversight Organization**.

- **Note:** You will also need to attach the documentation of Human Subjects Certification for each individual, if they have completed the certification somewhere other than Duke.
- If outside key personnel will have access to Duke PHI, a data transfer agreement AND external site IRB approval (or IRB authorization agreement) will be needed. See HRPP policy Use of Research Data by Former Duke Students or Former Duke Faculty and Employees
- In the panel below, "PHI" is Protected Health Information.

Entry 1		
	Name	
	Study Role	
Em	ail Address	
Institution / O	rganization	
Will he/she have D	e access to uke P.H.I.?	O Yes 💿 No
Is he/she volunteer at D	an unpaid uke on the study?	O Yes 💿 No

### Indicate the Protocol source below:

The protocol source is the author of the protocol. If the protocol is a joint authorship between multiple sources, select the primary author.

An IRB fee may be assessed for all research that is supported by for-profit entities and requires full board review. For additional information, see the **IRB fees section of the IRB web site** 

- PI initiated
- Commercial / Industry (for-profit entity) initiated
- C Federal Government initiated
- C Cooperative Group Initiated
- O Foundation (non-profit group) initiated
- 🔿 Other

### **Sponsor and Funding Source**

### Add all funding sources for this study:

View Details	Sponsor Name		Sponsor Type	Contract Type:	Project Number	Award Number	
	National Institute on Drug Abuse		Federal Government	Grant			
Sponsor Name:		National Institute on Drug Abuse					
Sponsor Type: F		Federal Government					
Sponsor Role:		Funding					
Grant/Contract Number:		P50DA027840					
Project Period: Fro		From:08/15/2015 to:05/31/2020					
Is Institution the Primary Grant							

Holder:	Yes					
Contract Type:		Grant				
Project Number:						
Award Number:						
Grant Title:	Cen	Center for Adaptive Treatment of Cigarette Addiction				
PI Name: (If PI is not the same as identified on the study.)						
Explain Any Significant Discrepancy:						
Principal Investigator		Duke	Grant			
Sponsor Name:	Prin	cipal Investigator				
Sponsor Type:	Duk	e				
Sponsor Role:	Prot Cen	cocol Control Data Coordination N ter;	1onitoring	Coordinatir	ng	
Project Period:	From	m:08/15/2015 to:05/31/2020				
Is Institution the Primary Grant Holder:	Yes	Yes				
Contract Type:	Gra	nt				
Project Number:						
Award Number:						
Grant Title:						
PI Name: (If PI is not the same as identified on the study.)						
Explain Any Significant Discrepancy:						
Is this a federally funded study?						
⊙ Yes O No						

 
Does this study have any of the following?
 
Industry sponsored protocol
 
Industry funded Duke protocol
 
Industry funded sub-contract from another institution
 
Industry provided drug/device/biologic
 
SBIR/STTR funded protocol
 
						
O Yes 💿 No						
As part of this study, will any samples or PHI be transferred to/from Duke to/from anyone other than the Sponsor, a Sponsor subcontractor, or a Funding Source?						
○ Yes ⊙ No						

Is the Department of Defense (DOD) a funding source?

### For Federally funded studies:

Is your funding subject to, and does it comply with, the funding agency's policy for data sharing?

🔿 Yes 💿 No

### Enter the Grant Number or Other Federal Agency Proposal or Application Number:

P50DA027840

**Note:** The Federal Funding Agency ID Number is the Sponsor's grant number assigned to your project and available on your Notice of Award (example: R01HL012345).

### If known, enter the SPS (Sponsored Projects System) number if applicable:

230139

### In the Initial Submission Packet, attach the following:

(1) The entire grant, or an explanation of why a grant is not needed.

(2) NIH institutional Certificate form related to data sharing (if applicable).

The entire grant is needed so that it may be reviewed against the protocol for concordance.

Have you successfully synced your protocol to OnCore by clicking the 'Sync Data Over API' button at the top of this page?

Please verify that the protocol has been created in OnCore before submitting this application for PI Signoff.

• Yes, I synced my protocol to OnCore and verified it was successfully sent by logging into OnCore.

O I may have forgotten! I'll click it again right now, just to be sure, and verify it was successfully sent by logging into OnCore.

### **Mobile Devices and Software**

Does this study involve the use of a software or a mobile application?

🔿 Yes 💿 No

List all software, including third party (non-Duke) and mobile apps, that will be utilized for ascertainment, recruitment, or conduct of the research/project: (eg, MaestroCare, DEDUCE):

Microsoft Access is used for logging subject information (Enrollment Log, Visit Log, etc.); this database is designed and maintained by the CRC ([name], [contact]), and data are entered by key personnel. Main [contact].

The Study Team will design CRFs in REDCap. Study participants will complete some study questionnaires on REDCap. Questionnaires will be completed within REDCap on a desktop computer in the office. The technician will log on to the REDCap site and will open the questionnaires for the subjects. Subjects will only have access to their questionnaires. Access to any other websites will be blocked by Psychiatry Information Technology. Remote participants will complete all surveys/questionnaires online via REDCap.

Other questionnaires will be completed on paper forms which were designed in Microsoft Word and Excel 2010.

We intentionally do not record calls and we do not allow for generic user input or long 'voicemail' style inputs. We require callers spell and pronounce their names and key in a telephone number to prevent excess unnecessary information from being collected.

Zoom will be used to verify the identity and date of birth of participants. It will also be used to verify CO readings. Zoom calls will not be recorded.

Multi-site Research							
Is this a multi-site study?							
O Yes 💿 No							
Complete for each site if Duke is the Primary grant awardee or coordinating center:							
Entry 1							
Site Name:							
City:							
State/Province:							
Country:							
	Site Contact Information						
Primary Contact Name:							
Primary Contact Phone:							
Primary Contact Email:							
	Site Details						
Does the site have an IRB?	O Yes O No						
Site IRB approval expiration date:							
If date not provided, explanation of why:							
Has the site granted permission for the research to be conducted?	O Yes O No						
Does the site plan to rely on the DUHS IRB for review?	O Yes O No						
What is the status of the study at this site?	O Open O Closed						
Site approval letters or site							

personnel lists:

### **Research Abstract**

### Please type your Research Abstract here:

The Research Abstract should summarize the main points of your study in one paragraph. The following guidelines may help you:

- 1. Purpose and objective (1-2 sentences)
- 2. Study activities and population group (2-4 sentences)
- 3. Data analysis and risk/safety issues (1-2 sentences)

We propose to assess the relative role of nicotine dose and route of delivery in affecting successful switching from combustible cigarettes to e-cigarettes, as well as concomitant reductions in ad libitum cigarette smoking and exposure to harmful and potentially harmful constituents of combustion. The strategy will be to assess adoption of e-cigarette use and concomitant reduction in ad libitum smoking of subjects' usual brands of cigarettes over an 8-week period, during which they will receive nicotine or non-nicotine e-cigarettes, and nicotine skin patches. The nicotine patches will not be used as a therapeutic treatment in this study, but rather as a way to manipulate the nicotine dose, while varying the rate and route of nicotine delivery. Behavioral or "habit" aspects of e-cigarette use will be controlled for by the groups receiving non-nicotine e-cigarettes. One hundred thirty daily cigarette smokers will be randomly assigned to receive 8 weeks of exposure to the following conditions (65/group):

- 1. Nicotine containing e-cigarettes + 21 mg nicotine skin patches
- 2. Zero-nicotine e-cigarettes + 21 mg nicotine skin patches

The time commitment for subjects is 8 weeks once their participation begins, plus one follow-up session at four weeks. Subjects will return every two weeks to obtain e-cigarette and patch supplies, and for outcome measures of e-cigarette and combustible cigarette use to be collected; alternatively, remote partipants will be sent supplies in two shipments and will complete study questionnaires online. Ad libitum smoking will be assessed weekly using daily diary recordings of cigarettes smoked per day as well as the objective index of expired air carbon monoxide (CO) levels measured at the study visits.

The primary outcome measures will be the amount of combustible cigarette use and e-cigarette use in the last week of the 8-week exposure period. The main index of combustible cigarette use will be expired air CO. Self-reported cigarettes/day recorded on diaries will be a secondary index of cigarette consumption. The main index of e-cigarette use will be the number of cartridges consumed, based on self-report and counts of the number of unused e-cigarette tanks returned.

Continuing to smoke carries significant health risks. Subjects enrolling in this study are not being asked to quit smoking over the course of the study, but will be exposed to no additional risk from their usual smoking behavior. Their exposure to harmfully and potentially harmful constituents in combustible cigarettes may decrease to the extent they use e-cigarettes as an alternative to combustible cigarettes.

### **Research Summary**

### State your primary study objectives

We propose to assess the relative role of nicotine dose and route of delivery in affecting successful switching from combustible cigarettes to e-cigarettes, as well as concomitant reductions in *ad libitum* cigarette smoking and exposure to harmful and potentially harmful constituents of combustion.

The strategy will be to assess adoption of e-cigarette use and concomitant reduction in *ad libitum* smoking of subjects' usual brands of cigarettes over an 8-week period, during which they will receive nicotine or non-nicotine e-cigarettes, and nicotine skin patches. The nicotine patches will not be used as a therapeutic treatment in this study, but rather as a way to manipulate the nicotine dose, while varying the rate and route of nicotine delivery. Behavioral or "habit" aspects of e-cigarette use will be controlled for by the groups receiving non-nicotine e-cigarettes.

### State your secondary study objectives

### Please select your research summary form:

### Standard Research Summary Template

This is the regular (generic) research summary template which is required for all regular applications (unless your protocol fits under the other research summary templates in this category). Use of these instructions is helpful for ensuring that the research summary contains all necessary elements.

### **Standard Research Summary**

**Purpose of the Study** 

Objectives & hypotheses to be tested

We propose to assess the relative role of nicotine dose and route of delivery in affecting successful switching from combustible cigarettes to e-cigarettes, as well as concomitant reductions in *ad libitum* cigarette smoking and exposure to harmful and potentially harmful constituents of combustion.

The strategy will be to assess adoption of e-cigarette use and concomitant reduction in *ad libitum* smoking of subjects' usual brands of cigarettes over an 8-week period, during which they will receive nicotine or non-nicotine e-cigarettes, and nicotine or non-nicotine skin patches. The nicotine patches will not be used as a therapeutic treatment in this study, but rather as a way to manipulate the nicotine dose, while varying the rate and route of nicotine delivery. Behavioral or "habit" aspects of e-cigarette use will be controlled for by the groups receiving non-nicotine e-cigarettes.

We hypothesize that e-cigarette use will be higher, and concomitantly, combustible cigarette use will be lower, in the nicotine e-cigarette condition compared to the zero-nicotine e-cigarette condition (i.e., comparing Group 1 vs. Group 2).

### **Background & Significance**

Should support the scientific aims of the research

Cigarette smoking remains the leading cause of preventable disease and death in developed countries, due principally to its contributions to heart disease, chronic obstructive pulmonary disease (COPD), and cancer (Lando & Wilson, 2010). The annual death toll in the U.S. from diseases caused by smoking has been increasing steadily and is estimated to be the highest ever, 540,000/year (Carter et al., 2015).

The U.S. Surgeon General's Report of 2010 (USDHHS, 2010) concluded that the combustion products of smoke, rather than nicotine, were responsible for most smoking related diseases. E-cigarettes, which deliver nicotine in the absence of combustion, have been advanced as a tobacco harm reduction strategy. Thus far, however, only a minority of smokers have adopted e-cigarettes to satisfy their nicotine dependency without concurrent use of combustible cigarettes. A number of factors may serve as barriers to the adoption of e-cigarettes, including insufficient dose of nicotine and lack of familiar sensory/habit components (e.g., aroma, "throat hit") associated with smokers' usual brands of cigarettes. The present study will examine the relative roles of nicotine dose and route of administration in affecting the ability of smokers to transfer their dependency from combustible cigarettes (CC) to e-cigarettes.

There are several reasons why administration of a given dose of nicotine by inhalation (via e-cigarettes), vs. transdermal administration (via nicotine patches) would be more reinforcing and lead to greater switching from combustible cigarettes to e-cigarettes. First, inhaled nicotine reaches the bloodstream and brain much faster than transdermal administration (Rose et al., 2010), producing immediate reinforcing

effects. Also, inhaled nicotine produces familiar respiratory tract cues that smokers find rewarding (Rose, 2006). Indeed studies have reported a greater suppression of combustible cigarette use when smokers used e-cigarettes as an alternative compared with nicotine patch (McRobbie et al., 2014).

Although subjects receiving nicotine from e-cigarettes will no doubt receive a range of nicotine doses, depending on the extent of use, data from previous studies (Shahab et al., 2017) suggests that the mean dose is expected on average to be similar to that provided by a 21 mg/day patch (and actual mg/day, as estimated from the number of e-liquid cartridges consumed, will be a covariate in the statistical analyses.).

### **Design & Procedures**

Describe the study, providing detail regarding the study intervention (drug, device, physical
procedures, manipulation of the subject or the subject's environment, etc.). Discuss justifications for
placebo control, discontinuation or delay of standard therapies, and washout periods if applicable.
Identify procedures, tests and interventions performed exclusively for research purposes or more
frequently than standard of care. Include alternative therapies, concurrent therapies discontinued per
protocol, risk benefit ratio, and use of tissue/specimens. Discuss monitoring during washout periods if
applicable. Include brief description of follow-up, if any.

### Design Overview

The study will comprise a randomized, double-blind parallel-arm study to ascertain the role of nicotine dose and route of administration in reducing use of combustible cigarettes and in facilitating adoption of e-cigarettes. One hundred thirty daily cigarette smokers will be randomly assigned to receive 8 weeks of exposure to the following conditions (65/group):

- 1. Nicotine containing e-cigarettes + 21 mg nicotine skin patches
- 2. Zero-nicotine e-cigarettes + 21 mg nicotine skin patches

Nicotine and non-nicotine e-cigarettes will be purchased from JUUL Labs. The JUUL is a rectangular closedsystem e-cigarette. This e-cigarette was commercially available as of August 8, 2016 and does not contain any alterations to the chemistry or physical characteristics. Each JUUL Pod pack contains 4 pods. Each JUUL Pod contains 0.7mL with 5% nicotine by weight, approximately equivalent to one pack of cigarettes or 200 puffs. Multiple flavors will be used in this study in order to more accurately mimic real world conditions. Subjects will receive packs containing tobacco-flavored and mint-flavored or menthol-flavored pods. Subjects will be provided with enough additional packs of pods to use during the smoking period. JUUL Pods are sealed system cartridges for use in the JUUL e-cigarette. Each pod is contained in tamper resistant blister packs. The nicotine patches will be purchased from Duke Outpatient Pharmacy.

Ad libitum smoking will be assessed weekly using daily diary recordings of cigarettes smoked per day as well as the objective index of expired air carbon monoxide (CO) levels measured at the study visits.

### Screening and Session Procedures

Interested potential subjects will respond to advertisements by contacting our Center to be phone screened. Potential subjects also will have the option to complete a REDCap screening survey on the Duke Center for Smoking Cessation website. Potential subjects will be given a brief description of the study and will be asked questions to assess eligibility and interest. Eligible subjects interested in participating will be scheduled for the screening visit.

After granting their informed consent, potential subjects will complete a smoking history form and will have their expired air CO measured. Subjects will provide a urine sample for testing of illicit drug use (all participants) and for pregnancy (women of child bearing potential only). Potential subjects will fill out the Medical History Form and Review of Systems Form on REDCap, as well as asked about any other medical issues they are aware of, on the revised Preliminary Contact Form. A Physician Assistant will review this information with the potential participant either during the screening visit or during a brief (approx. 15 minute) phone call. The screening visit will last approximately 1.5 hours.

The time commitment for subjects is 12 weeks once their participation begins. Subjects will return every two weeks (for eight weeks -- i.e., 5 visits) to obtain e-cigarette and patch supplies, and for outcome measures of e-cigarette and combustible cigarette use to be collected. Four weeks after Study Visit 5, subjects will return for one follow-up session.

### Sessions

The first study visit (V1) will take place approximately one week after the screening visit. Subjects will complete baseline questionnaires and will be randomized to one of the two groups. Subjects will be tested for exhaled air carbon monoxide, and saliva samples will be collected for analysis of smoking related chemicals (e.g., cotinine). Subjects will also complete questionnaires assessing their dependence on cigarettes (Fagerström Test for Nicotine Dependence (FTND) (Heatherton et al., 1991)), and rewarding effects of cigarettes (modified Cigarette Evaluation Questionnaire (Cappelleri et al., 2007)).

Subsequent study visits will occur approximately two weeks apart (with a five-day window on either side of the scheduled visit). If a participant does not attend a visit and it cannot be rescheduled within the allowable window, the visit will be considered a missed visit; if participants miss two consecutive visits they will be withdrawn from the study. Participants will be tested for exhaled air carbon monoxide, and will also complete questionnaires assessing their dependence on cigarettes (Fagerström Test for Nicotine Dependence (FTND) (Heatherton et al., 1991)), and rewarding effects of cigarettes (modified Cigarette Evaluation Questionnaire (Cappelleri et al., 2007)).

Questionnaires will be completed within REDCap on a desktop computer in the Center office. The technician will log on to the REDCap site and will open the questionnaires for the subjects. Subjects will only have access to their questionnaires. Access to any other websites will be blocked by Duke Psychiatry Information Technology.

At the first (V1) and final (V5) sessions, participants will provide saliva and urine samples. The saliva sample will be used for analysis of smoking related chemicals (e.g., cotinine). The urine sample will be used to assess total urinary 4-(methylnitrosamino)-1-(3-pyridyl)-1-butanol (NNAL), a metabolite of the tobacco-specific carcinogen 4-(methylnitrosamino)-1-(3-pyridyl)-1-butanone (NNK). The half-life of NNAL is 10 days (Goniewicz et al., 2009), yielding a valuable index of sustained reductions in cigarette smoking. The half-life of expired air CO, in contrast, is 4.5 h (Sandberg et al., 2011). Total urinary nicotine equivalents (a measure of total nicotine intake) will also be assessed.

Subjects will also be given diaries to record the number of cigarettes smoked each day and e-cigarette cartridges used, and will be instructed to return the diaries at the next visit. At Sessions V1-V4, participants will be dispensed a sufficient supply of skin patches and e-cigarette refill tanks (pods) to last until the next session. Participants will be given pods with both flavors (Virginia tobacco and cool mint or menthol) of e-liquid. They will be asked to return all used and unused pods and used patches at their subsequent visit for proper disposal and compliance monitoring.

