Randomization and E-cigarette Distribution: After the 1-week training/baseline period is complete and any concerns or questions about the CO monitoring have been addressed, the participants will be assigned a participant number that will determine their randomly assigned study condition, and will be sent by study staff the first shipment of study patches and e-cigarette devices and cartridges containing e-liquid corresponding to their group assignment (nicotine containing e-cigarettes vs. zero-nicotine e-cigarettes). Packages containing nicotine patches and e-cigarettes and liquids require signature by someone who is 21 years of age or older for delivery; the packages will not be delivered if no one appropriate is available to sign for them. This supply will be designed to last through the first 4 weeks of the study; if participants remain in the study, they will be sent a second shipment to use for the final 4 weeks.

Study Milestones: Remote participants will complete study milestones ("e-visits") that correspond to the study visits attended by local participants: baseline, week 2, week 4, week 6 and week 8, plus 4-week follow-up; they will take approximately one hour each to complete and include the same questionnaires that are completed at the in-person study visits, as well as a CO measurement at e-visit 5. The first (baseline) study milestone (V1) will take place after the participants receive their first shipment of e-cigarettes but before they start using them. At this time, participants will be called by study staff and given instructions on how to use the e-cigarettes. They will be asked to switch from cigarette use to use of e-cigarettes during the study. They will then be instructed on the use of daily self-report diaries to be completed on paper. In these diary entries, participants will record the number of conventional cigarettes smoked each day and the number of occasions of e-cigarette use (an occasion defined as taking at least one puff). Participants will be emailed a survey link to complete the questionnaires online via REDCap. Participants will have 72 hours to complete the survey until it expires and it is considered a "missed milestone"; if participants miss two consecutive milestones they will be withdrawn from the study. The

diary entries will be reported to the research staff by phone after e-visit online surveys have been completed.

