### **Data Analysis & Statistical Considerations**

 Describe endpoints and power calculations. Provide a detailed description of how study data will be analyzed, including statistical methods used, and how ineligible subjects will be handled and which subjects will be included for analysis. Include planned sample size justification. Provide estimated time to target accrual and accrual rate. Describe interim analysis including plans to stop accrual during monitoring. Phase I studies, include dose escalation schema and criteria for dose escalation with definition of MTD and DLT.

The primary outcome measures will be the amount of combustible cigarette use and e-cigarette use in the last week of the 8-week exposure period. The main index of combustible cigarette use will be expired air CO, a highly sensitive and specific measure of smoke inhalation. As a secondary measure (at the first (V1) and final (V5) sessions), we will assess total urinary 4-(methylnitrosamino)-1-(3-pyridyl)-1-butanol (NNAL), a metabolite of the tobacco-specific carcinogen 4-(methylnitrosamino)-1-(3-pyridyl)-1-butanone (NNK). The half-life of NNAL is 10 days (Goniewicz et al., 2009), yielding a valuable index of sustained reductions in cigarette smoking. The half-life of expired air CO, in contrast, is 4.5 h (Sandberg et al., 2011).

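### Withdrawing participants from the study after two consecutive missed visits can close off the week-8 primary outcomes for people who could still be measured, with possible bias of unknown size and direction.

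*Combined protocol and SAP*

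**What the plan says.** For in-person participants, Sessions places randomisation at V1: "Subjects will complete baseline questionnaires and will be randomized to one of the two groups". Later visits are two weeks apart, "with a five-day window on either side of the scheduled visit". A visit not held within that window counts as missed, and "if participants miss two consecutive visits they will be withdrawn from the study".

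For remote participants, Remote Study Participation (Study Milestones) says: "Participants will have 72 hours to complete the survey until it expires". After that the milestone counts as missed, and "if participants miss two consecutive milestones they will be withdrawn from the study". The paragraph on return and re-use of the CO monitor says a second monitor is sent for e-visit 5 to those who were accepted and completed e-visits 1 to 4. The opening of that section limits remote CO readings to screening and e-visit 5.

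Data Analysis & Statistical Considerations defines the primary outcomes as the "amount of combustible cigarette use and e-cigarette use in the last week of the 8-week exposure period". Expired-air CO is the main index of smoking. Cartridges consumed, from self-report and counts of unused tanks returned, is the main index of e-cigarette use. The section names a general linear model with covariates, but no analysis population, no handling of withdrawn participants and no missing-data method. The Data Safety Monitoring Plan asks only that reasons for missing data be recorded. No attrition rate is given anywhere.

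**The concern.** The rule removes people from the study, not merely from product supply, and it acts on behaviour after randomisation. Study visits are also where in-person participants collect supplies, so someone who has rejected the assigned e-cigarette and gone back to usual smoking has less reason to attend. The plan itself predicts lower e-cigarette use and more smoking in Group 2 (zero-nicotine), so the people lost could differ between arms in number, in week-8 smoking, or both.

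At stake is whether the week-8 comparison describes those randomised or only those who stayed engaged with their product. If Group 2 loses more continuing smokers, the benefit of nicotine e-cigarettes is understated. If Group 1 loses more, for example through side effects, it is overstated, and the one-sided test would reject too often.

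**Working it through.** **1. When the rule itself costs V5.** Each of V2 to V5 is attended (A) or missed (M), which gives 16 patterns. These are counts of patterns, not probabilities.
- Eight contain two consecutive misses and trigger withdrawal.
- In six of the eight the pair is V2+V3 or V3+V4, so withdrawal comes before V5. In three of these six (MMAA, AMMA, MMMA) the participant would have attended V5.
- In the other two (AAMM, MAMM) the only consecutive pair is V4+V5. V5 was already missed, and the rule costs at most late retrieval and the 4-week follow-up.
- Remote track, read literally: four further patterns (AAMA, AMAA, MAAA, MAMA) do not trigger withdrawal and include e-visit 5, but fail the condition for being sent the monitor. One missed e-visit is enough to lose the week-8 CO.

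**2. The plan's own figure.** Inputs from Data Analysis & Statistical Considerations: effect 0.5 SD, one-sided alpha 0.05, 50 per group, power at least 80%. Power = Φ(0.5 × √(50/2) − 1.645) = Φ(0.855) = 80.4%, so the figure reproduces (noncentral t: 79.9%). With all 65 per group (Design Overview) it is Φ(0.5 × √(65/2) − 1.645) = Φ(1.205) = 88.6%. This is an upper bound on what full follow-up could give. The gap between 65 and 50 equals 1 − 50/65 = 23.1%. It may be an allowance for loss, but the documents do not say so.

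**3. Size of a possible bias.** Let q1 and q2 be the proportions lost in Groups 1 and 2, and let k be the amount, in SD, by which the week-8 smoking of those lost exceeds that of completers (same k in both arms). Each full-arm mean is the completer mean plus q × k, so

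completer benefit = true benefit − (q2 − q1) × k.

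Assumed inputs, since the documents give none: |q2 − q1| = 0.05 to 0.15 and k = 0.5 to 1.0.
- Lowest: 0.05 × 0.5 = 0.025 SD, which is 5% of 0.5.
- Highest: 0.15 × 1.0 = 0.15 SD, which is 30% of 0.5.
- If only half of those withdrawn would have come to V5, the part due to the rule is, to a first approximation, half: 0.0125 to 0.075 SD, or 2.5% to 15% of 0.5.

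**4. Effect on the test.** Assume 30 of 130 lost and k = 0.25 to 1.0.

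| Lost, Group 1 / Group 2 | Shift in benefit (SD) | Power at true 0.5 | One-sided type I error |
|---|---|---|---|
| 15 / 15 | 0 | 80.4% | 5% |
| 10 / 20 | −0.04 to −0.15 | 74% to 53% | 3.3% to 0.8% |
| 20 / 10 | +0.04 to +0.15 | 85% to 95% | 7.3% to 19.0% |

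Equal loss is not safe if k differs by arm. With 15 lost in each, and k = 0.5 in one arm and 0 in the other, the shift is 15/65 × 0.5 = 0.12 SD. Power is then 61% if the gap is in Group 2, and type I error is 14.3% if it is in Group 1.

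**The case against.** Several limits on this point stand.
- A reader might infer that the rule loses the week-8 outcome of everyone it withdraws. It does not: where only V4+V5 are the missed pair, V5 was gone already. The rule matters only for people who missed visits over about a month and would still have come to V5, and the documents do not say how many that is. They also leave undefined which data collection stops on withdrawal. That nothing more is collected is an inference from the wording and the absence of any later provision.
- A reader might infer that such participants have no data after baseline. In person, CO is taken at every visit and diaries and pods are returned, so someone lost after V2 still has V2 data. What is missing is the week-8 value. This reply is weaker for remote participants, who have no CO reading between screening and e-visit 5.
- A reader might infer that the 72-hour remote limit, against five days either side in person, itself biases the arms. It does not: whether a person takes part remotely is settled before randomisation, and an online survey and a clinic visit are not equal burdens.
- A reader might take 0.15 SD as the expected bias. Every input is assumed, that end needs a large imbalance between arms, and the formula credits the rule with all loss among those withdrawn.

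The larger number randomised may protect power, but it does not protect against bias.

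**Conclusion.** The point holds in this form. Followed as written, the plan gives up week-8 primary data from participants who miss V2+V3 or V3+V4 but could still be measured. On a literal reading it also gives up the week-8 CO of any remote participant who misses one of e-visits 1 to 4. The loss follows randomisation and may depend on product acceptance, so it can bias the comparison.

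The documents do not support saying that it will, or in which direction. The illustrative ceiling is 0.025 to 0.15 SD if everyone withdrawn is retrievable, and about half that if half are. It rests on an assumed 5 to 15 point difference between arms and an assumed gap of 0.5 to 1.0 SD, equal in both arms. The change should be made because it is cheap and because week-8 measurements not taken cannot be recovered at analysis.

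**What to change.** - **Sessions and Study Milestones:** leave product dispensing as it is now, but replace withdrawal from the study with continued outcome follow-up. Invite every randomised participant who has not withdrawn consent to V5 or e-visit 5 for CO, diary or recall of cigarettes and cartridges, return or count of pods, and the urine and saliva samples. The cartridge items need explicit mention for remote participants, whose diaries record occasions of use rather than cartridges.
- **Return and Re-use of the CO monitor:** remove completion of e-visits 1 to 4 as a condition for sending the week-8 monitor.
- **Data Analysis & Statistical Considerations:** state that all V5 data obtained are analysed by assigned arm. Name the analysis population, the missing-data method and a sensitivity analysis, because some participants will still not return.

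The cost is a short amendment with matching consent wording. For each participant who returns there is one further visit payment, a sample kit and, if remote, a monitor shipment. From Subject Compensation, payments at V5 are up to $25 + $10 = $35 in person and up to $25 + $5 + $5 + $50 = $85 remotely, the $50 being for return of the monitor. Some V5 data will come from people no longer using study product. That is a real downside for describing effects under use, but those data belong in a comparison of the groups as randomised.
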